8.0 ADVERSE EVENTS REPORTING

All suspected adverse events (AEs) will be reported to the Study Safety Monitoring Desk at the Stanford Center for Clinical Research (SCCR) by the Study Telehealth Provider Team. The Study Safety Monitoring Desk will review all suspected AEs and determine relatedness to the device (related to the IRN feature, Apple Watch ECG app, or ePatch) and seriousness.

8.1 Definitions and Classification

Term	Definition	Reference
Adverse Event (AE)	Any untoward medical occurrence, unintended disease or injury, or untoward clinical signs (including abnormal laboratory findings) in participants, users or other persons, whether or not related to the device.	ISO 14155-1
Serious Adverse Event (SAE)	Adverse event that 
 a) Led to death, b) Led to serious deterioration in the health of the participant, that either resulted in 
 1) A life-threatening illness or injury, or 2) A permanent impairment of a body structure or a body function, or 3) In-patient or prolonged hospitalization, or 4) Medical or surgical intervention to prevent life-threatening illness or injury or permanent impairment to a body structure or a body function, c) Led to fetal distress, fetal death or a congenital abnormality or birth defect 	ISO 14155-1

8.2 Adverse Events (AEs)

This document contains information that is privileged or confidential and may not be disclosed unless such disclosure is required by applicable laws and regulations. The information in this document is the property of Apple Inc. and may not be reproduced, published, or disclosed to others without written authorization from Apple Inc.

The Study Safety Monitoring Desk is responsible for determining whether the adverse event occurred and is related to the IRN feature, ECG app on Apple Watch, ePatch, or associated with participation in the study.

Possible AEs include the following:

- Skin rash due to wearing the ambulatory ECG monitor (ePatch);
- Skin itchiness due to wearing the ambulatory ECG monitor (ePatch);
- Blister due to wearing the ambulatory ECG monitor (ePatch);
- Skin rash on wrist due to wearing the Apple Watch;
- Pressure artifacts on wrist due to wearing the Apple Watch;
- Signs or symptoms related to use of the IRN feature or ECG app on Apple Watch. The common signs and symptoms include stress and anxiety and associated symptoms that may include dizziness, depression, palpitations, tremors, sleep difficulty, and shortness of breath.

The following occurrences are not to be regarded as AEs:

- Underlying (pre-existing) symptoms or diseases, unless there is an increase in severity or frequency during the course of the investigation;
- Receipt of an IRN;
- Detection of atrial fibrillation or other irregular heartbeat through the IRN feature or ECG App;
- Detection of atrial fibrillation or other irregular heartbeat through ePatch;
- Pre-planned procedure(s);
- Complaint about iPhone or Apple Watch functionality;
- Failure of the participant to regularly wear the Apple Watch or to wear the ePatch
- Apple Heart Study 1.2 app, IRN feature, ECG app, and ePatch functionality issues that do not allege an adverse event

8.3 Serious Adverse Event

If an event is determined by the Study Safety Monitoring Desk to be related to the IRN feature, ECG app, or ePatch, the Study Safety Monitoring Desk will further investigate the event for classification as a Serious Adverse Event.

8.4 Reporting of Suspected Device-Related Serious Adverse Event

8.4.1 Related to IRN feature or Apple Watch ECG App

This document contains information that is privileged or confidential and may not be disclosed unless such disclosure is required by applicable laws and regulations. The information in this document is the property of Apple Inc. and may not be reproduced, published, or disclosed to others without written authorization from Apple Inc.

Possible adverse events related to the IRN feature or ECG app will be reported to the sponsor within 2 business days of being reviewed by the Study Safety Monitoring Desk. The Study Safety Monitoring Desk will conduct further investigation of these events and determine seriousness. The investigation of these events will be completed and reported to the sponsor within 20 days of initial report to sponsor.

8.4.2 Related to ePatch

Events confirmed to be Serious Adverse Events and related to the ePatch will be reported to the BioTelemetry by the Study Safety Monitoring Desk.

8.5 Reporting of Adverse Events (AEs) to IRB

Adverse events will be promptly reported to the IRB if they meet the definition of an Unanticipated Problem (UP), as defined in section 12.1. Timeframes for UP reports are as follows:

1. Within 10 working days from when the Stanford study team learns of the event
2. Within 5 working days from when the Stanford study team learns of the event for unexpected deaths or life-threatening experiences related to the research.

This document contains information that is privileged or confidential and may not be disclosed unless such disclosure is required by applicable laws and regulations. The information in this document is the property of Apple Inc. and may not be reproduced, published, or disclosed to others without written authorization from Apple Inc.

9.0 WITHDRAWAL

Every participant should be encouraged to remain in the study until they have completed the protocol-required follow-up period. If the participant withdraws prematurely from the study, the reason for withdrawal should be documented. Possible reasons for premature withdrawal may include, but are not limited to the following:

- Withdrawal of consent: participant decides to withdraw from the study for any reason. This may be concluded if/when a participant taps the withdraw button within the app or asks to be withdrawn.
- Investigators believe it is in the best interest of the participant to discontinue the study, for any reason.
- It is discovered that participant does not meet inclusion/exclusion criteria

Withdrawal Process:

Participants will have the option to withdraw from the study by tapping a “Withdraw from Study” button within the app. This will disable notifications and will result in a cessation of data collection. If a participant calls the Study Telehealth Provider requesting withdrawal from the study, the Study Telehealth Provider will instruct the participant how to initiate withdrawal on the app. It will not be possible for any party other than the study participant themselves to withdraw from the study. In the few cases where the participant has initiated contact with the Study Telehealth Provider, and thereafter selects “Withdraw from Study” on the app, they may still receive follow-up communication from the Study Telehealth Provider. In order to stop further communication, these participants would need to inform the Study Telehealth Provider Team that they wish to be withdrawn.

Once withdrawn, participants would be able to re-enroll only by reinstalling the application, but will be considered a new study participant without linkage to their prior data.

The following will be considered lost-to-follow-up:

- Death of the participant
- Lost/stolen iPhone and/or Apple Watch

This document contains information that is privileged or confidential and may not be disclosed unless such disclosure is required by applicable laws and regulations. The information in this document is the property of Apple Inc. and may not be reproduced, published, or disclosed to others without written authorization from Apple Inc.

10.0 STATISTICAL CONSIDERATIONS

10.1 Analysis Sets

All analyses will be reported for the overall cohort, as well as by cohort status determined at enrollment: (1) Irregular Rhythm Notification, and status of (2) Afib or (3) Inconclusive via the ECG app (i.e., with at least 1 ECG recorded within the 14 days before study enrollment indicating classification of either AFib or Inconclusive, where the latter is defined as “Inconclusive,” “Heart Rate Over 120,” or “Heart Rate Under 50”).

The Full Analysis Set (FAS) will consist of all enrolled participants who complete the informed consent process. This analysis set will be used to summarize subject demographics, medical history, adverse events, self-reported health status, diagnosis, and contact with the health care provider.

The ePatch eligible analysis set (EEAS) will consist of those in the FAS deemed eligible to receive an ePatch at Study Visit #1.

The ePatch Analysis Set (EAS) will consist of all those in the EEAS who receive and return an ePatch with at least 1 hour of usable data and who do not belong to the Fallout Group.

The Fallout Subgroup Analysis Set (FOG) will consist of participants meeting the criteria of Section 7.10. Demographic and medical history information will be presented for this analysis set.

Objectives 1a, 1b, and 2b and 2c will be conducted using the EAS, whereas Objective 2a will be conducted using the EEAS. The analyses for Objectives 1a, 1b, and 2b and 2c will be repeated in the EEAS as a sensitivity analysis using appropriate methods for handling missing data.

10.2 Outcomes and Definitions

10.2.1 Primary Outcome

Atrial fibrillation or atrial flutter of at least 30 seconds duration on an ambulatory ECG patch monitor for a participant who received an IRN or Apple Watch ECG app-AFib classification prior to enrollment.

10.2.2 Secondary Outcomes

1. Arrhythmias other than AF on an ambulatory ECG patch monitor
2. Self-reported contact with a non-study healthcare provider

10.3 Statistical Approaches to Outcome Analyses

This document contains information that is privileged or confidential and may not be disclosed unless such disclosure is required by applicable laws and regulations. The information in this document is the property of Apple Inc. and may not be reproduced, published, or disclosed to others without written authorization from Apple Inc.

There are no pre-specified statistical hypotheses in this clinical study. Descriptive statistics and 95% confidence intervals will be presented using available data as detailed below.

10.3.1 Primary Outcome Analyses

Objective 1a Analysis

This proportion will be estimated as the ratio of the number of participants in the EAS who have atrial fibrillation or atrial flutter of at least 30 seconds duration on patch wear and received an IRN before enrollment, divided by the number of participants in the EAS who received an IRN before enrollment. An exact 95% two-sided confidence interval will also be presented. We will also describe the number of participants who received an IRN before or during ECG enrollment with arrhythmias other than atrial fibrillation.

Objective 1b Analysis

This proportion will be estimated as the ratio of the number of participants in the EAS who have atrial fibrillation or atrial flutter of at least 30 seconds duration on patch wear and received an ECG app-AFib classification before enrollment divided by the number of participants in the EAS who received an ECG app-AFib classification before enrollment. An exact 95% two-sided confidence interval will also be presented. We will also describe the number of participants who received an ECG app-Fib before enrollment with arrhythmias other than atrial fibrillation.

10.3.2 Secondary Outcome Analyses

Objective 2a Analysis

This proportion will be estimated as the ratio of the number of participants who received an IRN or ECG app-AFib in the EEAS who reported contact with a non-study healthcare provider at 15 (and separately at 60) days after study enrollment divided by the number of participants in the EEAS who received an IRN or ECG app-AFib. An exact 95% two-sided confidence interval will also be presented.

Objective 2b Analysis

This proportion will be estimated as the ratio of the number of participants in the EAS who have atrial fibrillation or atrial flutter of at least 30 seconds duration on patch wear and received an ECG app-Inconclusive status before enrollment, divided by the number of participants in the EAS who received an ECG app-Inconclusive status before enrollment. An exact 95% two-sided confidence interval will also be presented. We will also describe the

This document contains information that is privileged or confidential and may not be disclosed unless such disclosure is required by applicable laws and regulations. The information in this document is the property of Apple Inc. and may not be reproduced, published, or disclosed to others without written authorization from Apple Inc.

number of participants who received an ECG app-Inconclusive status before enrollment with arrhythmias other than atrial fibrillation.

Objective 2c Analysis.

This proportion will be estimated as the ratio of the number of participants who have atrial fibrillation or atrial flutter of at least 30 seconds duration on patch wear who are greater than 65 years of age at enrollment divided by the number of participants enrolled who are greater than 65 years of age at enrollment using the EAS. An exact 95% two-sided confidence interval will also be presented. We will also describe the number of participants who are 65 years of age or older at enrollment with arrhythmias other than atrial fibrillation.

A similar proportion will be presented for those less than 65 years of age at enrollment.

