10.4 Handling of Missing Data

This document contains information that is privileged or confidential and may not be disclosed unless such disclosure is required by applicable laws and regulations. The information in this document is the property of Apple Inc. and may not be reproduced, published, or disclosed to others without written authorization from Apple Inc.

Participants who do not respond to the 15 or 60 day PROs, do not have at least an hour of analyzable wear time from the ambulatory ECG monitor or do not return a patch within 45 days will be considered to have missing data. Methods for missing data such as multiple imputations will be implemented when performing analyses on the FAS or the EEAS. The assumptions of the missing data method will be evaluated in sensitivity analyses.

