3. ANALYSIS SETS

The Full Analysis Set (FAS) will consist of all enrolled participants who complete the informed consent process. This analysis set will be used to summarize subject demographics, medical history, adverse events, self-reported health status, diagnosis, and contact with the health care provider.

The ePatch Eligibility Analysis Set (EEAS) will consist of those in the FAS deemed eligible to receive an ePatch at Study Visit #1. This analysis set will be used to assess Objective 2a.

The ePatch Analysis Set (EAS) will consist of all those in the EEAS who receive and return an ePatch with at least 1 hour of usable data and who do not belong to the Fallout Subgroup. This analysis set will be used to assess Objectives 1a, 1b, and 2b and 2c. We will repeat these analyses in the EEAS as a sensitivity analysis using appropriate methods for handling missing data.

The Fallout Subgroup Analysis Set (FOG) will consist of participants who enroll and complete the informed consent process but otherwise do not complete the study. Reasons for study incompleteness include; failure to contact Study Telehealth Provider within 30 days of enrollment, being deemed ineligible at Study Visit #1 for ePatch wear due to emergent symptoms, ePatch not returned within 45 days of enrollment, failure to start wearing ePatch within 14 days of shipment, unable to verify at Study Visit #1 a study eligible IRN or ECG-app notification, study withdrawal (i.e., withdrawal of consent), or lost to follow-up (i.e., death). We will present demographic and medical history information for this analysis set.

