4. ANALYSIS METHODS

4.1 General Principles

Method for Constructing Confidence Intervals

We will construct confidence intervals using the asymptotic Gaussian approximation. For proportions near 1 or 0, a potential drawback of this method is confidence intervals containing values outside of the range [0,1]. If we encounter confidence intervals with bounds outside of the [0,1] range we will instead construct the confidence intervals using the bias corrected and accelerated (BCa) method of creating a bootstrap confidence interval.

Incomplete Dates

If only the year of a date is given (YY), then the date shall be set to 'YY0701'. If only the year and month of a date is given (YYMM), then the date shall be set to 'YYMM15'.

Descriptive Statistics

Numerical variables will be summarized using standard summary statistics including the number of participants, mean, standard deviation, median, 10th and 90th percentile and range (i.e., minimum and maximum) as appropriate. For categorical data, proportions will be presented in a frequency table format.

Multiple Patches per Participant

In rare instances where a single user ID is associated with data available from more than one patch, only data from the final patch will be used in statistical analyses.

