4.3 Analysis Methods

Analysis of the Primary Endpoint Addressing Objective 1a and 1b

For Objectives 1a and 1b we have designed the study to estimate the proportion of participants diagnosed with AF within a 0.10 confidence interval width.

Objective 1a – The proportion of participants with an IRN prior to enrollment who have AF confirmed by ambulatory ECG patch monitoring.

This proportion will be estimated as the ratio of the number of participants in the EAS who have atrial fibrillation or atrial flutter of at least 30 seconds duration on patch wear and received an IRN before enrollment, divided by the number of participants in the EAS who received an IRN before enrollment. An exact 95% two-sided confidence interval will also be presented. We will also describe the number of participants who received an IRN before or during enrollment with arrhythmias other than atrial fibrillation.

Objective 1b Analysis – The proportion of participants with an ECG app-AFib classification prior to enrollment who have AF confirmed by ambulatory ECG patch monitoring.

This proportion will be estimated as the ratio of the number of participants in the EAS who have atrial fibrillation or atrial flutter of at least 30 seconds duration on patch wear and received an ECG app-AFib classification before enrollment divided by the number of participants in the EAS who received an ECG app-AFib classification before enrollment. An exact 95% two-sided confidence interval will also be presented. We will also describe the number of participants who received an ECG app-Fib before enrollment with arrhythmias other than atrial fibrillation.

Analysis of the Secondary Endpoints Addressing Objectives 2a, 2b and 2c

Objective 2a Analysis - The proportion of participants with an IRN or ECG app-AFib classification reporting contact with a non-study healthcare provider at 15 and 60 days after study enrollment.

This proportion will be estimated as the ratio of the number of participants who received an IRN or ECG app-AFib classification in the EEAS who reported contact with a non-study healthcare provider at 15 (and separately at 60) days after study enrollment divided by the number of participants in the EEAS who received an IRN or ECG app-AFib. An exact 95% two-sided confidence interval will also be presented.

Objective 2b Analysis

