4.6 Handling of Missing Data

Participants who do not respond to the 15 or 60 day PROs, do not have at least an hour of analyzable wear time from the ambulatory ECG monitor or do not return a patch within 45 days will be considered to have missing data. We will use methods for missing data such as multiple imputation when performing analyses on the FAS or the EEAS. We will further evaluate the assumptions of missing data methods in sensitivity analyses.

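### Objective 2a: the literal ratio counts PRO non-responders as no contact, and the plan does not say whether its missing-data rule overrides it; the 2c formula says over 65 where the objective is 65+ (minor)

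*Combined protocol and SAP*

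**What the plan says.** **Objective 2a.** Protocol section 10.3.2 divides reported contacts at day 15, and separately at day 60, by the whole notified group: "divided by the number of participants in the EEAS who received an IRN or ECG app-AFib". SAP section 4.3 repeats this, with a numerator of participants "who received an IRN or ECG app-AFib classification in the EEAS who reported contact with a non-study healthcare provider". Both attach an exact two-sided 95% interval. Neither limits the denominator to people who answered the questionnaire.

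**Missing PROs.** Protocol section 10.4 and SAP section 4.6 list non-response to the 15- or 60-day PRO as missing data. The protocol continues: "Methods for missing data such as multiple imputations will be implemented when performing analyses on the FAS or the EEAS". The SAP says: "We will use methods for missing data such as multiple imputation when performing analyses on the FAS or the EEAS". Both add that the assumptions will be examined in sensitivity analyses. The EEAS is the main analysis set for 2a.

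**Objective 2c.** The objective (protocol section 2.2, SAP section 1.1) splits age at enrollment into under 65 and 65+. The formula in protocol section 10.3.2 and SAP section 4.3 has as its denominator "the number of participants enrolled who are greater than 65 years of age at enrollment using the EAS", and the companion proportion is for those under 65. In the same paragraph, the count of other arrhythmias covers people aged 65 or older.

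**The concern.** A PRO non-responder can never enter the 2a numerator but always enters its denominator. Followed literally, the formula treats silence as no contact, while the missing-data sections say that silence is missing data. The same data then give two different contact proportions, and the 2a paragraph does not say which will be reported. The interval adds to the doubt: an exact binomial interval needs one integer count out of n, and an estimate pooled over imputations has no such count.

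Facilitating clinical evaluation is half of the overall research question (protocol section 2.1), and 2a is its measure. Under the literal ratio, a lower response at day 60 than at day 15 would by itself lower the day-60 figure.

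For 2c, if age is held in completed years, the two AF strata do not add up to the EAS. The AF and other-arrhythmia results for the older group would then describe different people.

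**Working it through.** The documents state no expected rate, sample size or precision for 2a or 2c, so there is no planned figure to reproduce. All rates below are assumptions.

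**2a: size of the gap.** Let r be the PRO response rate, c the contact rate among responders and c' the contact rate among non-responders.

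- Literal ratio: r × c.
- Proportion in the whole group: r × c + (1 − r) × c'.
- Shortfall: (1 − r) × c'. If non-responders resemble responders (c' = c), this is c × (1 − r), whatever the sample size.

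| Assumed response | c = 30% | c = 60% |
|---|---|---|
| 90% | 27%, gap 3 points | 54%, gap 6 points |
| 80% | 24%, gap 6 points | 48%, gap 12 points |
| 60% | 18%, gap 12 points | 36%, gap 24 points |

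The percentages in the cells are the literal ratio. If response were 80% at day 15 and 60% at day 60 with contact unchanged, the ratio would drop by 0.2 × c, that is from 24% to 18% or from 48% to 36%.

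**2a: gap against the stated precision.** Take N = 800, the number reached if both exclusive targets of 400 are met (protocol section 10.5); the actual 2a denominator is not given. Exact (Clopper-Pearson) intervals at 80% response, so 640 responders:

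- c = 30%: literal 192/800 = 0.240 (0.211 to 0.271); responders only 192/640 = 0.300 (0.265 to 0.337).
- c = 60%: literal 384/800 = 0.480 (0.445 to 0.515); responders only 384/640 = 0.600 (0.561 to 0.638).

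In both cases the literal interval excludes the responder-only estimate.

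**2a: what imputation gives.** With an assumed n = 1000, 70% contact and 80% response, and data missing at random:

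- literal ratio: 0.560 (exact 0.529 to 0.591);
- responders only: 0.700 (exact 0.667 to 0.732);
- multiple imputation, 500 imputations, Rubin's rules: 0.699 (0.667 to 0.731).

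The ratio can be computed in each imputed data set and pooled, so a ratio and imputation are compatible. What does not carry over is the exact interval, because the pooled variance includes a between-imputation part.

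**2a: cost in width.** At N = 800, the responder-only width over the literal width is (0.337 − 0.265)/(0.271 − 0.211) = 0.072/0.060 = 1.20 at 30% contact, and (0.638 − 0.561)/(0.515 − 0.445) = 0.077/0.070 = 1.10 at 60%. In the n = 1000 example the Rubin's-rules width, 0.731 − 0.667 = 0.064, is close to the responder-only width, 0.732 − 0.667 = 0.065.

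**2c.** Side by side: the objective is <65 and ≥65; the AF formula is <65 and >65; the other-arrhythmia count is ≥65. In completed years, everyone aged 65 is in neither AF stratum. The shift in the older stratum's AF proportion is w × d, where w is the share of the 65+ group aged 65 and d is the AF difference between age 65 and 66+. Assuming w = 5-10% and d = 5-20 points gives 0.05 × 5 = 0.25 to 0.10 × 20 = 2.0 points. Protocol section 5.1 takes age from date of birth; with exact age, only someone enrolled on the 65th birthday is lost.

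**The case against.** The best defence is that the plan already deals with PRO non-response. It names these non-responders as missing and calls for missing-data methods on the EEAS, and 2a is the one objective whose main analysis is on the EEAS. This stands: the missing-data rule is the natural one for 2a, and applying it need not leave any bias. What it does not supply is a statement in the 2a paragraph that the rule applies, or an interval that fits.

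Protocol section 10.3 also says that estimates use the data available, as detailed in what follows. That could support a responder-only estimate with an exact interval. It does not settle the matter, because the detail that follows sets the whole notified EEAS group as denominator.

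Three stronger readings are tempting but not supported:

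- A reader might infer that the ratio and the missing-data rule are irreconcilable. They are not: the ratio can be pooled over imputations, and the plan's wording prescribes no single method. Only the exact interval fails to fit.
- A reader might infer that 2a was left out of the missing-data methods, because protocol section 10.1 says "The analyses for Objectives 1a, 1b, and 2b and 2c will be repeated in the EEAS as a sensitivity analysis" and does not name 2a. Those four objectives run on the EAS and are repeated on the EEAS. SAP section 3 says of the EEAS, "This analysis set will be used to assess Objective 2a", so for 2a there is nothing to repeat.
- A reader might add the SAP's general rule, "We will construct confidence intervals using the asymptotic Gaussian approximation", as a further 2a conflict. That mismatch with the exact intervals affects every objective and is a separate matter.

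It is also fair that the plan has no pre-specified hypotheses and no day-15 to day-60 comparison, and that the 2c intent is evident: the subgroup analyses, baseline categories and recruitment checks all use 65 and above.

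**Conclusion.** The point holds as a need for clarification. The 2a paragraph, followed literally, understates contact by the non-response share times the contact rate among non-responders. That is 6-12 points at an assumed 80% response and 30-60% contact, if non-responders resemble responders. If protocol section 10.4 and SAP section 4.6 are applied, this need not happen, and nothing shows that the sponsor intends otherwise. The remaining defect is that the plan does not say which rule gives the reported 2a figure and attaches an interval that suits only the literal or responder-only reading.

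The 2c formula contradicts its objective in both documents. The effect is about nil with exact age and probably small with completed years.

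Severity is minor: both are descriptive secondary objectives, and every rate used to size the effect is an assumption.

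**What to change.** **2a**, in protocol section 10.3.2 and SAP section 4.3:

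- State that the main estimate follows protocol section 10.4 and SAP section 4.6, and give a short imputation specification.
- Replace the exact interval with one that includes imputation variance (Rubin's rules).
- At days 15 and 60, report the PRO response rate and the responder-only proportion with its interval.
- Show the present ratio only as the lower bound in which non-response means no contact.

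Other choices of main estimate are defensible; what matters is that one is named with an interval that fits it.

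**2c**, in the same two sections: replace the over-65 wording by aged 65 or older, in numerator and denominator.

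**Cost:** no new data are needed. The work is a cross-reference, a brief specification, two table rows and a few words for 2c. The 2a interval becomes somewhat wider, about 10-20% at 80% response under the assumed rates.
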